7.6.1 Events Reported in the CRF/Study Database

Study staff will actively elicit and collect information about the occurrence of adverse events in a non-leading manner during the active collection period (as defined above), covering the time period beginning when the first protocol-required procedure is performed at Visit 1 and concluding 15 minutes after the procedure is performed. AEs identified as occurring during the active collection period may be based on symptoms or other complaints reported to the Investigator (or designee) by the participant, or may be based on clinical findings made by the Investigator (or designee).

The Investigator is required to assess whether these events are serious or non-serious, and whether or not they are related to study participation. All AEs that occur during the active collection period will

be collected in the clinical study database only via the CRF. These procedure-related events do not need to be sent to the Pfizer DSU.

If the participant withdraws from the study and also withdraws consent for the collection of future information, the active collection period ends when consent is withdrawn.

7.6.2 Medically Important RRI

Given this study only involves specimen collection using methods routinely used in clinical care (i.e., collection of urine, nasal swabs, and blood samples), no SAEs are anticipated. However, should a participant, in the investigator's opinion, suffer a medically important research related injury (RRI) caused by their participation in the study, the sponsor and designated Pfizer clinician or medical monitor must be notified immediately. A medically important RRI is any untoward medical occurrence that:

- Results in death;
- Is life-threatening (immediate risk of death);
- Requires inpatient hospitalization or prolongation of existing hospitalization;
- Results in persistent or significant disability/incapacity (substantial disruption of the ability to conduct normal life functions);
- Results in congenital anomaly/birth defect.

Medical and scientific judgment is exercised in determining whether an injury is an important medical event. An important medical event may not be immediately life-threatening and/or result in death or hospitalization. However, if it is determined that the event may jeopardize the participant or may require intervention to prevent one of the other outcomes listed in the definition above, the important medical event should be reported as a medically important RRI.

7.6.3 Vaccine-Related SAEs and Other Special Exposure Scenarios

AvonCAP study staff will also record SAEs related to the Pfizer-BioNTech COVID-19 vaccine, BNT1672b2, should the investigator (or designee) become aware of any such event during the course of the study.

SAEs that are explicitly related to receipt of BNT1672b2 vaccine will be reported to the Pfizer Drug Safety Unit (DSU) within 24 hours of awareness via the provided Pfizer SAE report form, if the investigator becomes aware of such an event at any time during the study.

This study recognizes that, although active solicitation of safety reports related to receipt of BNT162b2 vaccine is not required as part of this study, the sponsor/investigator/research team may incidentally become aware of reportable events, as described in this section, through **unsolicited** patient report. Examples of how this might occur included, but are not limited to:

- the study participant reports an event during enrollment, contacts the investigator or study staff **outside** of the active collection period
- the Investigator becomes aware of events explicitly related to BNT162b2 through medical record review performed for the purposes of study data collection.

The awareness date for the purpose of reporting an event to the Pfizer drug safety unit is the date that the Investigator (or designee) becomes aware of the presence of all 4 minimum reporting criteria (i.e. an identifiable subject, an identifiable reporter, an event meeting SAE or special exposure definition, and history of vaccination with BNT162b2 vaccine). If the Investigator becomes aware of additional information about the event following initial reporting, this additional information must also be reported in a follow up report within 24 hours of awareness. The Investigator may also be requested by the Pfizer DSU to obtain specific follow-up information in an expedited fashion. Furthermore, the research team will encourage study participants to report their vaccine-related AE or SAE to the MHRA via the Yellow Card system.

Special exposure scenarios, including Exposure During Breastfeeding [EDB], Occupational/Environmental exposure, medication errors and overdose related to BNT162b2, will be reported to the Pfizer DSU within 24 hours of awareness. Definitions and reporting instructions are included in the Safety Reporting Reference Manual.

Exposure during pregnancy (EDP) to the COVID-19 vaccines including BNT162b2 is not reportable as an individual safety report, unless there is an associated SAE. Since vaccine effectiveness by pregnancy status is an endpoint in the study, these exposures will be summarized in the clinical study report (CSR). No clinical data on the pregnancy will be collected as part of this study, but follow-up information may be requested by the Pfizer DSU if the case is also associated with an SAE.

BNT162b2 vaccine effectiveness is an AvonCAP study endpoint, so individual SAE reports for lack of efficacy will not be submitted to the Pfizer DSU as vaccine-related AEs. Vaccine effectiveness will be summarized in the CSR.

The definitions of an AE, SAE, RRI, LOE and special exposure scenarios can be found in the Safety Reporting Reference Manual.

8 Study procedures and clinical data – Non-Consented arm

Total duration of participation per participant will be approximately one month from date of admission.

8.1 Non-consented, Surveillance Admission Data Collection (Day 1)

Screening all potential participants (adult patients with respiratory symptoms and/or suspected COVID-19) for eligibility for the disease surveillance study. Every effort will be made to approach, discuss, and enrol participants in the consented study arm and seek their consent for collection and use of data. However, in patients in whom it is not practicable to do so, surveillance activity will be undertaken as outlined below. Participants should be enrolled as soon as feasible after admission (no later than 48 hours after admission if at all possible). Data collection will include the following activities:

- Screen patients against the inclusion/exclusion criteria of this protocol
- Enter standard of care data into eCRF for LRTD events

8.1.1 Admission data collection

Patients meeting screening criteria will have basic demographic and clinical data collected on an e-CRF. This will involve collection of the following data at admission:

- Patient details
- Eligibility checks – inclusion/ exclusion criteria components
- Date of hospitalization
- Demographics (age, gender, race/ethnicity, socioeconomic status estimated by postcode, vaccination [influenza/ PCV13/PPV23/COVID-19 and date of relevant administration], smoking status, alcohol/drug use)
- Details of present illness (symptoms, date of onset, vital signs on admission to hospital)
 - Used antibiotics/antivirals in the 14 days prior to admission
- Standard-of-care test results
 - Routine biochemistry and haematology test results on admission, including C-reactive protein and NT-proBNP, and blood group
- Hospitalization data:
 - Admission hospital
 - Dates and time of admission

- New York Heart Association (NYHA) Heart Failure Classification, Pneumonia Severity (CRB65 and PSI scores)
- Relevant Medical History and Major Comorbidities
- Rockwell Frailty Score and Charlson Comorbidity Index

8.2 Non-consented Patient Outcome measures

The follow-up information should be collected 1 month after enrolment or when the patient is discharged from hospital (whichever occurs later). At day 30 after admission, the following will be assessed and recorded in the CRF:

- Microbiological investigation results
 - Blood cultures.
 - Respiratory microbiology testing, including bacterial (eg, PCR and culture) and viral testing (eg, COVID19, RSV and influenza),
 - Pneumococcal testing (eg, BinaxNOW urine test),
 - Antibiotic resistance results for pneumococcal isolates
 - Sputum Gram stain results
- Hospitalization data:
 - Dates of discharge
 - ICU stay (yes/no)
 - Number of days in ICU
 - Mechanical ventilation and days of ventilator use
 - Requirement for new/increased haemofiltration
 - Non-invasive ventilation requirement and days of usage
- Vital status at Day 30 after enrolment:
 - Deceased, not recovered, recovered, recovered with sequelae, recovery ongoing, unknown
 - Date of death if under 30 days from admission
- Record final clinical/standard-of-care diagnosis for qualifying acute LRTD illness:
 - CAP – radiologically or clinically confirmed, acute bronchitis/LRTI, exacerbation of underlying chronic respiratory disease, LRTI not otherwise specified, congestive cardiac failure, empyema/lung abscess, non-infective process, and non-respiratory infection-related diagnosis.
- Cardiac complications through Day 30 after enrolment:

- ST- and non-ST elevation myocardial infarction, cerebrovascular accident, new episode of atrial fibrillation or other arrhythmia, venous thromboembolism, cardiovascular-related death
- Hospital related adverse events (e.g., falls in hospital and hospital-acquired infections)

The Principal Investigator or designee should make an assessment of final standard-of-care LRTD-related diagnosis if any discrepancy exists in the record. The Investigator is to also confirm, based on any existing or new information, if the participant had clinically and radiographically confirmed pneumonia.

8.3 Non-Consented arms Patient Outcomes: One-year mortality assessment on Day 365

The assessment may be completed 365 to 390 days after enrolment by medical record review, during a follow-up standard care visit and/or other means.

At day 365 after admission, the following will be assessed and recorded in the CRF:

- Vital status (alive or deceased) at Day 365 after enrolment
- If the participant is deceased, total survival days following enrolment

8.4 Ongoing clinical care

This is an observational epidemiological study collating and recording standard-of-care investigations and patient details in a consented study with enhanced diagnostic tests. As such, Avon CAP should not impact on any aspect of clinical care or other interventional trial in which the patient may be participating.

8.5 Research-related injury reporting

Given that this study is non-interventional and covers a period during which participants are under clinical care, Adverse Event data will not be recorded - except that which is pertinent to study data collection - and Serious Adverse Events will not be reported unless they are related to the patient's involvement in this study.

Any event that;

- Results in death;

- Is life-threatening (immediate risk of death);
- Requires inpatient hospitalisation or prolongation of existing hospitalisation;
- Results in persistent or significant disability/incapacity (substantial disruption of the ability to conduct normal life functions); OR,
- Results in congenital anomaly/birth defect.

and is judged by an Investigator to be possibly, probably or definitely related to the patient's participation in this study (i.e. the collection of their data) will be reported to the Sponsor within 24 hours and to the approving REC within 15 days of the study team becoming aware of it.

9 Study size and data analytics

9.1 Study size

Expected study size was calculated using both a retrospective coding data from 2018-2019, and a 21-day prospective audit of adult patients admitted to the Acute Medical Unit at NBT. It should be noted that both methods used to calculate estimated patient numbers were conducted in a time period before the COVID-19 pandemic. Both methods calculated an Avon CAP patient cohort approximately 7,000 adult patients per annum at NBT, and assuming all 2 hospital sites have similar patient numbers, the envisaged patient cohort before COVID-19 was 14,000 patients per annum. However, given the COVID-19 pandemic we expect a significantly large sample size, which is likely to approximate 23,000 patients per annum across the 2 sites. Number of adults in surveillance population is approximately 630,000, yielding expected LRTD incidence of >3,600 per 100,000 population annually (3.65 per 100 person years; 95% CI: 3.60 to 3.70).

9.2 Pneumonia and LRTD group classifications

LRTD participants will be classified by standard-of-care diagnoses extracted from the medical chart and using standardized case definitions (e.g., for radiologically confirmed CAP). Standardized case definitions not specifically referenced in the study objectives will be included in the Statistical Analysis Plan (SAP). Events with a final diagnosis of pneumonia by the treating clinician will be considered to have standard-of-care pneumonia diagnosis. A case of RSV is considered any patient with positive molecular test from any specimen type and/or RSV seroconversion defined as 4-fold rise in RSV antibody titers between acute/convalescent samples. Participants with pneumococcus identified through standard of care testing (aside from colonization specimens) and UAD1/2 and BinaxNOW will be considered to have pneumococcal infection. COVID-19 infection will be defined as any patient who has current infection confirmed via laboratory diagnostic testing (molecular, serological or other future test deemed clinically appropriate to determine current SARS-CoV-A infection). Alternatively, any individual who meets any future diagnostic criteria which are determined sufficient to confirm current SARS-CoV-A infection will also be deemed to have COVID-19.

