Abbreviations: SOC = standard of care; UAD = urine antigen detection assay; RSV= respiratory syncytial virus; RRI = research-related injury; CRB-65 = Confusion, Respiratory rate, Blood pressure, 65 years of age and older.

- Sample collection and interview activities shown in bold above will be undertaken for consented participants only.
- All participants in the consented enhanced diagnostic testing will have confirmation of their eligibility confirmed and be subsequently enrolled at Visit 1 / Day 1.
- At Visit 2 and 3, relevant changes to medical history since the last visit will be documented.
- Respiratory samples will be collected for RSV and other respiratory pathogen testing if such testing has not already been ordered or completed as part of standard-of-care testing. Details on the type and collection process for samples will be included in the laboratory manual. Another respiratory swab will be collected at the convalescent visit, only if the participant experienced a new ARI after hospital discharge.

- e. For those that consent to participate in the Serology subset, a blood sample will be collected for serologic testing. A remnant of an appropriate blood sample from standard of care testing can be used if appropriate for this use per laboratory manual specifications. For this subset of patients, an additional convalescent visit will take place approximately 22–60 days after enrolment for collection of a convalescent blood sample. However, effort should be made to schedule this visit as close to day 42 as possible. If subject has another enrolment qualifying acute LRTD event(s) prior to their convalescent visit, they will have acute serology specimen taken at each enrolment and only one convalescent serology visit will be completed 42 days after last acute specimen was taken.
- f. The applicable covid risk questionnaire will be completed for participants during relevant period, e.g. national lockdowns.

Non-consented arm

Collection of standard-of-care data will be done for all identified LRTD events in study hospitals and entered into the surveillance databases hosted by the Trusts.

Table 2. Comprehensive List of Information to be collected for non-consented arm.

Procedure / Assessment	First Data Collection	Second Data Collection	Third Data Collection
	Admission	Outcomes and Results	Mortality
	Day 1	Day 30	Day 365
Visit Window	Within 48 hours of admission	Day 30 to 45	Day 365
Surveillance	X		
Clinical symptoms	X		
Medical History ^a	X	X	

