3.2.4 RSV Infection

1. To determine the population-based incidence of RSV LRTI hospitalizations both overall and stratified by presence of underlying risk conditions
2. To describe the clinical and epidemiological characteristics and clinical outcomes of RSV-related LRTI hospitalizations both overall and stratified by presence of underlying risk conditions
3. To describe the proportion of LRTI caused by RSV in hospitalized patients both overall and stratified by presence of underlying risk conditions
4. To describe the difference between the population-based incidence of hospitalization, epidemiology, clinical presentation, and outcomes observed in RSV-positive adults versus those with other common respiratory viruses (eg, SARS-CoV-2 and influenza)
5. To determine the pathogen distribution rates of RSV, SARS-CoV-2, and other viral pathogens among adults admitted with congestive heart failure or chronic obstructive pulmonary disease exacerbations

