Enhanced Diagnostic Testing. Patients who meet all inclusion criteria and no exclusion criteria with informed consent will be enrolled in enhanced diagnostic testing portion of the study. At the time of their enrolment visit, participants will be interviewed (if possible) and a urine for pneumococcal testing and a swab for respiratory pathogen testing will be obtained in all participants (unless refused at time of collection or the patient's clinical status prevents collection, e.g. an anuric participant cannot provide urine). Aliquots from the urine specimens collected from study participants will be frozen and stored for subsequent shipment to Pfizer laboratories for urinary serotype-specific antigen detection (UAD) and BinaxNOW® testing. Additional testing may be conducted on these specimens or portions of these specimens that may be stored at the Bristol Biobank only after obtaining appropriate permissions.

All LRTD events will have additional information collected at 30 days. Additional information on the participants' final clinical diagnosis, vital status, and cardiovascular complications of their current illness (pneumonia patients only) will be collected.

Study duration. The study is expected to enrol for three consecutive years with an option to extend should additional epidemiological data be needed. Yearly or seasonal interim analyses may be conducted.

Serology subset. All participants in the enhanced diagnostic testing group will be offered participation in the serology subset, which will involve the following additional visits/procedures: 1) serology specimen at enrolment visit/V1 (may be salvaged from SOC specimen if appropriate specimen available), and 2) additional in-person visit at Day 42 to collect a blood specimen for convalescent serology and possibly another respiratory pathogen swab (the later only if another intercurrent acute respiratory illness has occurred). Participation will require signature of an annex to the main study informed consent.

UAD and Viral Testing Controls. An additional group of approximately 400 contemporaneous control participants without acute LRTD, comparable by age group and season to subject in the enhanced testing group, will be enrolled participation. These participants will be identified as adults who are:

3. Patients attending outpatient clinics in participating hospitals in specialties other than respiratory or cardiology OR

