7.2 Consented arm, Visit 2: Final diagnosis/Vital status assessment (Day 30)

The assessment may be completed 30 to 45 days after enrolment by phone call, medical record review, during a follow-up standard care visit and/or other means.

At day 30 after admission, the following will be assessed and recorded in the CRF:

- Record final clinical/standard-of-care diagnosis for qualifying acute LRTD illness
- Vital status (alive or deceased) at Day 30 after enrolment
- Cardiac complications through Day 30 after enrolment

The Principal Investigator or designee should make an assessment of final standard -of-care LRTD-related diagnosis if any discrepancy exists in the record. The Investigator is to also confirm, based on any existing or new information, if the participant had clinically and radiographically confirmed pneumonia.

7.2.1 Data collection at V2:

- Record RRIs
- Hospital-related adverse events (e.g., falls in hospital and hospital-acquired infections)
- Final standard of care/ clinical diagnosis of acute LRTD illness
- Vital status at Day 30
- Occurrence of cardiovascular events within 30 days of illness onset (pneumonia only):

- non-ST elevation myocardial infarction (NSTEMI)
- ST-elevation myocardial infarction (STEMI)
- cerebrovascular accident
- new episode of atrial fibrillation or other clinically significant arrhythmia
- deep venous thrombosis or pulmonary embolism
- new or worsening congestive heart failure
- cardiovascular-related death

7.3 Consented arm, Visit 3 [serology subset only]: Convalescent serology assessment on Day 45

For those enrolled in the Serology subset who have signed the related ICD Annex, a follow-up visit will be conducted approximately 45 days after enrolment (visit window: Day 22 – 60). If there is a low patient return rate for this follow-up visit, the study will consider whether home visits may be more convenient and better suited to patients in this study. If home visits are undertaken, they will be offered to participants as a visit option, and an appropriate time will be arranged after liaison between the participant and research team. The procedures undertaken during home visits will ensure that both study participants and research staff are appropriately protected in line with any Health and Safety regulations (e.g. PPI, sharps bins, etc.).

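### RSV cases found only by a convalescent titre rise must have survived to at least Day 22, so pooling them into RSV outcomes lowers RSV 30-day mortality; outcome analyses should use molecular cases

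*Protocol*

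**What the plan says.** Section 9.2 makes either of two routes sufficient for an RSV case: "any patient with positive molecular test from any specimen type and/or RSV seroconversion defined as 4-fold rise in RSV antibody titers between acute/convalescent samples".

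The second route needs a convalescent blood sample. Under Table 1, footnote e, for the serology subset "an additional convalescent visit will take place approximately 22–60 days after enrolment for collection of a convalescent blood sample". Section 7.3 says that "a follow-up visit will be conducted approximately 45 days after enrolment (visit window: Day 22 – 60"), while section 4.1 describes an "additional in-person visit at Day 42 to collect a blood specimen for convalescent serology". The subset is opt-in: "Participation will require signature of an annex to the main study informed consent". Section 7.3 also foresees that patients may not come back ("If there is a low patient return rate for this follow-up visit") and would then consider home visits. Table 2 lists no study serology for the non-consented arm.

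Vital status is recorded at Day 30 (sections 7.2 and 8.2). Section 3.2.4, item 2, describes the clinical outcomes of RSV-related LRTI. Item 4 describes differences in incidence, epidemiology, presentation and "outcomes observed in RSV-positive adults versus those with other common respiratory viruses (eg, SARS-CoV-2 and influenza"). Nothing in either item restricts RSV to molecular cases.

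**The concern.** For a seroconversion-only case, membership of the RSV group is settled by an event (giving a second sample) that cannot happen to someone who died before Day 22. At either target day it cannot happen to anyone who died by Day 30. A patient with RSV missed by the molecular test who dies early never enters the RSV group, while a similar patient who survives, has joined the subset and is resampled does. This is immortal time built into case status, and it overlaps the 30-day outcome.

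At stake are RSV 30-day mortality and, because sicker patients are less likely to be resampled, probably ICU use and length of stay. Section 5.1 itself notes that patients who die soon after admission may be missed by consent and tend to be the severe ones. The serology route cannot reach them.

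A second effect concerns item 4. If a comparator virus is identified by molecular testing alone, RSV has an extra detection route. That raises the RSV count relative to the comparator while its mortality is lowered.

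**Working it through.** **Plan's own figures.** The protocol gives no RSV rate, RSV mortality or serology-subset size, so there is no stated figure on this point to reproduce. Its only sizing figure (section 9.1) does reproduce: 23,000 / 630,000 = 3.65 per 100, with 1.96 × √23,000 / 630,000 = 0.047 per 100, giving 3.60 to 3.70. Nothing below depends on it.

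**Inputs from the protocol.** Either route suffices (9.2). The convalescent window is Day 22 to 60, with a target of Day 42 (4.1, 6.3.5, Table 1 footnote e) or Day 45 (7.3, Table 1). Vital status is taken at Day 30.

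**Assumed inputs.** f is the share of RSV cases found by seroconversion only. m is the 30-day mortality of RSV, taken as equal in patients detected and missed by the molecular test.

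**Step 1: no deaths by Day 30 among seroconversion-only cases.** This holds when the visit takes place at either target day. Pooled mortality = (1 − f) × m + f × 0, so the ratio to m is 1 − f.
- f = 5%: 0.95
- f = 10%: 0.90
- f = 20%: 0.80

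**Step 2: visit at the earliest day, Day 22.** Deaths on Days 22 to 30 remain possible. Let L be the fraction of 30-day deaths falling on those days, with m = 10% assumed. Mortality of a seroconversion-only case is then L × m / (1 − (1 − L) × m).
- L = 10%: 0.010 / 0.910 = 1.10%. At f = 20% the ratio is 0.80 + 0.20 × 1.10/10 = 0.82.
- L = 25%: 0.025 / 0.925 = 2.70%. At f = 20% the ratio is 0.80 + 0.20 × 2.70/10 = 0.85.

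An early visit softens the bias but does not remove it.

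**Step 3: how large might f be?** Let d be the fraction of RSV found by molecular test, s the share of survivors giving paired sera, and q the fraction of missed cases that seroconvert. With x = (1 − d)(1 − m) × s × q, f = x / (d + x). All of these are assumptions: d 60% to 90%, s 5% to 50%, q 80%, m 5% to 15%.
- High end (d = 0.6, s = 0.5, m = 0.05): x = 0.4 × 0.95 × 0.5 × 0.8 = 0.152; f = 0.152 / 0.752 = 20%.
- Low end (d = 0.9, s = 0.05, m = 0.15): x = 0.1 × 0.85 × 0.05 × 0.8 = 0.0034; f = 0.0034 / 0.9034 = 0.4%.

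The mortality ratio therefore runs from about 0.80 to about 1.00.

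**Step 4: case count against a comparator found by molecular test only.** With equal true incidence and equal molecular sensitivity, the apparent incidence ratio is 1 / (1 − f): 1.05 at f = 5%, 1.11 at 10%, 1.25 at 20%. This applies only if the comparator has no serological route.

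**Step 5: after the change.** With one admission-episode molecular definition for all viruses, f = 0. Under no true difference and equal molecular sensitivity, both ratios return to 1.00.

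**The case against.** The strongest reply has four parts.

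*The share may be tiny.* Consented participants get a study RSV swab if none was taken in routine care, although they may decline it. Serology needs a separate annex, low return is foreseen, and the non-consented arm has no study serology. This stands: f could be well under 5%, and shares above about 20% are hard to reach even with generous assumptions.

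*The between-virus asymmetry is not fixed in this document.* A reader might infer that RSV alone has a serological route, so that the contrast with influenza and SARS-CoV-2 is biased by construction. The protocol does not support that. Section 9.2 allows COVID-19 to be confirmed serologically, although it specifies no paired convalescent rise. Influenza has no case definition in the protocol and may receive one in the SAP. Section 7.3 describes the convalescent blood as serving respiratory pathogen serology in general, with RSV included. This part is therefore conditional.

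*Seroconversion serves the study's aim.* Section 1.5 says RSV burden is underestimated and that enhanced testing should characterise it more fully. A reader might infer that seroconversion should be dropped from the RSV definition altogether. That does not follow: counting a fourfold rise suits the incidence objective, and the survivor bias concerns outcomes.

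*Mortality is not named for RSV, and home visits are possible.* Section 3.2.4 speaks of outcomes and description; 30-day mortality is a named objective only for COVID-19 and for LRTI with its pneumococcal subcategories. Both observations are correct. But Day 30 vital status is collected for every event and is an obvious RSV outcome, and a home visit removes the travel, not the need to be alive.

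None of the four touches the conditioning of seroconversion-only cases on survival, which section 9.2 fixes.

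**Conclusion.** The point holds for RSV outcomes. Seroconversion-only cases have survived to at least Day 22, and in most permitted visit timings past Day 30, so including them biases RSV 30-day mortality downward by a factor of about 1 − f. That is 0.95 at an assumed 5% and 0.80 at an assumed 20% (0.82 to 0.85 with some deaths on Days 22 to 30). The direction follows from the definition, given comparable underlying risk in patients detected and missed by the molecular test. The size rests on f, which the protocol does not give, and may be negligible. Cases with a positive molecular test at admission are unaffected.

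For the contrast in section 3.2.4, item 4, the safe statement is that ascertainment differs between viruses unless their case definitions are aligned. The document does not establish that the contrast with influenza or SARS-CoV-2 is wrong as planned. Nor does it show that the RSV incidence count in item 1 should lose its serological cases.

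**What to change.** Add to section 9.2, or to the analysis definitions for section 3.2.4:
- For RSV mortality, ICU use, length of stay and other outcome figures (items 2 and 4), and for the whole between-virus contrast in item 4, define RSV and each comparator virus by a positive molecular test on a specimen from the admission episode. The restriction to that episode matters because section 9.2 accepts any specimen type, and a further swab is taken at the convalescent visit after a new respiratory illness. A positive result on that swab would again require survival and return, and could reflect a later infection.
- Report seroconversion-only RSV cases separately, with their outcomes not pooled.
- Keep the 9.2 definition, including seroconversion, for RSV incidence (3.2.4, item 1), showing the count by detection route, and for the concordance objective (3.3.2, item 1).

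The change needs no new data or visits. Its cost is a somewhat smaller RSV case count in the outcome analyses, by the fraction f, and the loss there of patients whom the molecular test missed.
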